8.3. Missing Data

The data after the receipt of rescue therapy will be handled before imputation as below:

Use of rescue therapy: Except OC, all efficacy data on or after the receipt of rescue therapy will be considered as 'not evaluable data' for analysis. For analysis purpose it will be replaced by the worst possible score for endpoint, and considered as 'treatment failure'. However, in OC analysis, all observed data even after the receipt of rescue treatment will be included for analysis, i.e. no imputation for missing data.

In case of diary data, if the date of rescue therapy use is within the analysis visit window, the subject at the analysis visit will be treated as treatment failure except for OC analysis, and the weekly average will be imputed using the worst case value.

Further details for the data handling for rescue therapy are in section 7.

The primary method to impute the missing values will be as follows:

Continuous Endpoints: For continuous endpoints during Initial Period, the MI under MAR assumption approach and the MMRM approach will be used to handle the missing data for the selected secondary endpoints.

CCI

Binary Endpoints: All missing values will be treated as a non-responder for the binary endpoints for primary, key secondary and secondary endpoints during Initial Period. To assess the robustness of non-responder analysis for primary and key secondary endpoints, a tipping point analysis will be performed. The MI under MAR assumption, LOCF, and OC will be used as sensitivity analysis to impute the missing values for the primary and key secondary endpoints.

Adverse events and concomitant medications/procedures: Missing assessment times will have imputed times for the purposes of assessing treatment emergence for AEs or classifying medications/procedures into prior/concomitant. However, the assessment times (start date, stop date, and time if collected from CRF) without imputation will be presented in the listings.

For the start of a concomitant medication/procedure or AE:

- Only the year is reported: If the subject received the first study drug dose in the year reported, then the date of the first dose of study drug will be used as the start date; otherwise, January 1 of the year reported will be used as the start date.

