10.3.1. Investigator’s Global Assessment (IGA)

The IGA is a 5-point scale ranging from 0 (clear) to 4 (severe) used by the investigator or trained designee to evaluate the global severity of AD and the clinical response to a treatment (see Table 10-2).

Table 10-2: Investigator Global Assessment Scale

This document is confidential.

Statistical Analysis Plan for Interventional Studies

Sponsor: Galderma Research & Development, LLC; Protocol No.: RD.06.SPR.118169

Status	Score	Definition
Clear	0	Minor, residual hypopigmentation/hyperpigmentation, no erythema or induration/papulation, no oozing/crusting.
Almost clear	1	Trace faint pink erythema, with barely perceptible induration/papulation and no oozing/crusting.
Mild	2	Faint pink erythema with mild induration/papulation and no oozing/crusting.
Moderate	3	Pink-red erythema with moderate induration/papulation with or without oozing/crusting.
Severe	4	Deep or bright red erythema with severe induration/papulation with oozing/crusting.

IGA success is defined as 0 (clear) or 1 (almost clear) on the IGA scale and a ≥ 2 -point reduction from Baseline.

During Initial Period:

IGA will be collected at Screening, Baseline, Week 4, Week 8, Week 12, Week 16 and Early termination of the Initial Period.

IGA will be summarized as a categorical and continuous variable at each analysis visit. Absolute change from Baseline for the IGA score will also be presented in the summary for ITT and PP population.

IGA success will be calculated using Initial Period Baseline as the reference point for change on the IGA scale. The proportion of subjects with IGA success (OC, non-responder, LOCF) will be summarized.

Line plot for proportion of subject with IGA success using Non-responder imputation will be presented for Initial Period on the ITT population.

The number and percentage of subjects with IGA success and the number and percentage of subjects who achieved IGA success and an improvement of PP NRS ≥ 4 from Baseline will be analyzed up to Week 12 for the ITT population using non-responder.

The estimate of treatment unadjusted and strata-adjusted differences with the corresponding 2-sided 95% confidence intervals, and p-values from the Cochran-Mantel-Haenszel test will be presented.

During Maintenance Period:

IGA will be collected at Week 20, Week 24, Week 28, Week 32, Week 36, Week 40, Week 44, Week 48 and Early termination of the Maintenance Period.

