IGA will be summarized as a categorical and continuous variable at each analysis visit. Absolute change from Baseline and from Week 16 will be also presented in the summary for the ITT population.

IGA success will be calculated using Baseline and Maintenance Baseline (Week 16) as the reference point for change on the IGA scale. The proportion of subjects with IGA success will be summarized using OC, Non-responder and LOCF.

Line plot for proportion of subject with IGA success from Baseline using Non-responder imputation will be presented for Maintenance Period on the ITT population.

For the subset of subjects achieving IGA success at Week 16, the proportion of subjects maintaining IGA success at each visit throughout the Maintenance Period will be summarized. 'Maintaining IGA success'

This document is confidential.

is defined if achieved IGA success at every analysis visit until the analysis visit summarized. For example, if a subject achieved IGA success until Week 28 except Week 24, this subject will not be counted as 'Subjects maintained IGA success' at Week 28.

The number and percentage of subjects who achieved IGA success and an improvement of PP NRS ≥ 4 from Week 16 will be summarized for the ITT population using OC and for the subset of subjects with such a response at Week 16.

No hypothesis testing will be performed for Maintenance Period.

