EASI-50/75/90 will be calculated using Baseline as the reference point for change in EASI score. The proportion of subjects achieving EASI-50/75/90 (OC, non-responder, LOCF) will be summarized on ITT population. And the results using OC will be provided for PP population.

For the proportion of subjects with EASI-50/75/90 (non-responder) and subjects with EASI-75 and PP NRS improvement ≥ 4 (non-responder), the estimate of treatment unadjusted and strata-adjusted differences with the corresponding 2-sided 95% confidence intervals, and p-values from the Cochran-Mantel-Haenszel test will be presented.

Line plot for proportion of subject with EASI-50/75/90 from Baseline using Non-responder imputation will be presented for Initial Period on the ITT population.

Individual components of the EASI score (averaged across body regions) will be summarized as continuous variables. Change from Baseline in individual components of the EASI score will also be presented in the summary table.

Change from Baseline in individual components of the EASI (averaged across body regions) at each analysis visit up to Week 16 will be analyzed using MMRM. For the MMRM analyses the least squares means (LSMeans), standard error of LSMMeans, and 95% CI for change from Baseline, as well as the difference in LSMMeans between the treatment groups, the two-sided 95% CI, and associated p-value will be presented.

During Maintenance Period:

EASI will be collected at Week 20, Week 24, Week 28, Week 32, Week 36, Week 40, Week 44, and Week 48 of the Maintenance Period.

EASI will be summarized as a continuous variable at each analysis visit. Absolute change and percent change from Baseline and Maintenance Baseline (Week 16) in EASI at each analysis visit up from Week 16 to Week 48 will also be summarized.

EASI-50/75/90 will be calculated using Baseline and Maintenance Baseline (Week 16) for change in EASI score. The proportion of subjects with EASI-50/75/90 will be summarized using OC, non-responder and LOCF.

Line plot for proportion of subject with EASI-50/75/90 from Baseline using Non-responder imputation will be presented for Maintenance Period on the ITT population.

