"Itch-free days" will be defined if PP/AP NRS score is 0 or 1. The proportion of "itch-free days" will be calculated using 7 days diary data for the visit. A minimum of 4 daily scores out of the 7 days for the visit is required for the proportion calculation. The proportion of "itch-free days" will be calculated using number of days of PP/AP NRS score of 0 or 1 divided by number of days reported during the week. The summary of proportion of "itch-free days" based on PP NRS/AP NRS will be presented for Initial Period.

During Maintenance Period:

PP/AP NRS will determined by an average using 7 days data before the visit for Week 24, Week 32, Week 40, Week, Week 48 as a continuous variable for the Maintenance Period. Absolute change and percent change from Baseline and Maintenance Baseline (Week 16) for the PP/AP NRS score will also be included in the summary. No hypothesis testing will be performed.

Improvement in PP/AP NRS will be calculated using Baseline and Maintenance Baseline (Week 16) as the reference point for change in PP/AP NRS score. The proportion of subjects with an improvement of PP/AP NRS ≥ 4 and the proportion of subjects with a PP/AP NRS < 2 will be summarized.

For the subset of patients achieving an improvement of PP/AP NRS ≥ 4 at Week 16, the proportion of subjects achieved such an improvement at each analysis visit during the Maintenance Period will be summarized. For the subset of patients achieving a PP/AP NRS < 2 at Week 16, the proportion of subjects with PP/AP NRS < 2 at each visit during the Maintenance Period will be summarized using OC.

Line plot for proportion of subjects with PP NRS improvement ≥ 4 and for proportion of subjects with PP NRS < 2 using Non-responder imputation will be presented for Maintenance Period on the ITT population.

CCI

[figure not shown]
Approved 10-Nov-2022 00:00:00

This document is confidential.

Statistical Analysis Plan for Interventional Studies

Sponsor: Galderma Research & Development, LLC; Protocol No.: RD.06.SPR.118169

CCI

1.0

CD14152.SPR118169.SAP.V01

Approved 10-Nov-2022 00:00:00

[figure not shown]
This document is confidential.

CCI

1.0

[figure not shown]
CD14152.SPR118169.SAP.V01

Approved 10-Nov-2022 00:00:00

This document is confidential.

CCI

[figure not shown]
1.0

CD14152.SPR118169.SAP.V01

Approved 10-Nov-2022 00:00:00

This document is confidential.

CCI

[figure not shown]
1.0

CD14152.SPR118169.SAP.V01

Approved 10-Nov-2022 00:00:00

This document is confidential.

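### Maintenance IGA success referenced to Week 16 cannot be met by subjects re-randomised at IGA 0 or 1, so that version does not measure maintenance

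*SAP*

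**What the plan says.** SAP 10.3.1 opens its definition with "IGA success is defined as 0 (clear) or 1 (almost clear) on the IGA scale" and adds a reduction of at least 2 points from Baseline. For maintenance it then says "IGA success will be calculated using Baseline and Maintenance Baseline (Week 16) as the reference point for change on the IGA scale", summarised by observed case (OC), non-responder imputation and LOCF. SAP 8.2 makes the Week 16 value the Maintenance Baseline, and SAP 6.1 makes the maintenance ITT population all re-randomised subjects. Under Protocol 8.1 a nemolizumab subject is re-randomised on IGA 0 or 1, or EASI-75, at Week 16.

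The same double reference appears for the other responder outcomes:

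- SAP 10.3.2: "EASI-50/75/90 will be calculated using Baseline and Maintenance Baseline (Week 16) for change in EASI score".
- SAP 10.3.3: "Improvement in PP/AP NRS will be calculated using Baseline and Maintenance Baseline (Week 16) as the reference point for change in PP/AP NRS score", with improvement of at least 4 points as the responder criterion.

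The composites of IGA success or EASI-75 with itch improvement (SAP 10.3.1 and 10.3.2) are described as a response "from Week 16 will be summarized for the ITT population using OC and for the subset of subjects with such a response at Week 16". The summary of maintained IGA success names no reference point. Protocol section 7 treats Week 16 as baseline for maintenance endpoints only where applicable.

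**The concern.** Most re-randomised subjects have little or no room left on the scale, because a good Week 16 result is what admitted them. A criterion that asks for a further 2-point IGA fall from Week 16 cannot register that they held their response. A low rate in such a table could be read as loss of effect when it only reflects where subjects started. Maintenance efficacy is the secondary objective, the maintenance endpoints are also to be pooled with a second pivotal trial (Protocol section 7), and SAP section 2 says the planned analyses will enter regulatory submissions and/or manuscripts. A reader who meets the table without a clear label may therefore be misled.

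**Working it through.** **The plan's own maintenance count.** Protocol 8.1 uses 750 subjects randomised 2:1, 15% dropout, and responder rates of 45% and 12%.

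- Nemolizumab: 500 × 0.85 × 0.45 = 191.25 (stated 190).
- Placebo: 250 × 0.85 × 0.12 = 25.5 (stated 26).
- Total: 216.75 (stated 216). The count reproduces.

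**IGA rule, enumerated.** Success requires a score of 0 or 1 and reference minus score of at least 2.

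| Reference IGA | Largest possible fall | Later scores that count as success |
|---|---|---|
| 0 | 0 | none |
| 1 | 1 | none |
| 2 | 2 | 0 only |
| 3 | 3 | 0 or 1 |
| 4 | 4 | 0 or 1 |

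With Week 16 as reference, rows 0 and 1 are 0% by construction. With initial Baseline as reference, only rows 3 and 4 occur, because entry requires IGA of at least 3; a subject who stays at 0 or 1 is then a success.

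**How many are affected.** Since entry requires IGA of at least 3, IGA 0 or 1 at Week 16 is the same as IGA success, planned at 30%. EASI-75 is planned at 49% (both Protocol 10.2). Entry to maintenance is the union of the two:

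share at IGA 0/1 = 0.30 / (0.30 + 0.49 − overlap)

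- Full overlap (0.30): 0.30 / 0.49 = 61%, or 116 of 190. Highest attainable Week 16-referenced rate: 1 − 0.61 = 39%.
- No overlap (0): 0.30 / 0.79 = 38%, or 72 of 190. Highest attainable rate: 1 − 0.38 = 62%.

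These caps are reached only if every other subject improves enough: to 0 from IGA 2, or to 0 or 1 from IGA 3 or 4.

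Taking the 45% responder rate of Protocol 8.1 as denominator gives 0.30 / 0.45 = 67%. But a union cannot be smaller than one of its parts, so 45% does not fit with 49% EASI-75.

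**Pruritus NRS.** The scale stops at 0, so a Week 16 score below 4 rules out a further 4-point improvement. The documents do not say how many subjects this covers.

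**EASI.** The Week 16 version is attainable (undefined only at a Week 16 EASI of 0), but it asks a different question. A subject exactly at EASI-75 at Week 16 needs, relative to initial Baseline:

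- EASI-50 from Week 16: 1 − 0.25 × 0.50 = 87.5%.
- EASI-75 from Week 16: 1 − 0.25 × 0.25 = 93.75%.
- EASI-90 from Week 16: 1 − 0.25 × 0.10 = 97.5%.

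**Composites and maintained success.** In the composites, Week 16 may be the reference or merely the first visit of a range. SAP 10.3.2 uses similar words as a range for EASI change: "at each analysis visit up from Week 16 to Week 48 will also be summarized". The subset defined by such a response at Week 16 points to initial Baseline, since change from Week 16 is zero at Week 16 itself. The same reasoning applies to the subset used for maintained IGA success. Neither passage says so. If Week 16 were the reference, both IGA versions would be unattainable for subjects at IGA 0 or 1.

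**The case against.** The strongest reply is that nothing is lost. The quoted sentence also plans the Baseline-referenced version, in which a subject who stays clear is a success. SAP 10.3.1 adds categorical IGA at each visit, a Baseline-referenced line plot with non-responder imputation, and a maintained-success summary. The maintenance line-plot titles for IGA, EASI and NRS improvement in the SAP figure index name initial Baseline. The protocol allows a Week 16 reference where applicable, and further improvement is a fair question for subjects who entered on EASI-75 alone or with residual itch. Maintenance is descriptive throughout, and the maintenance efficacy table titles are redacted, so their labels cannot be checked.

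Most of this stands, and it limits the point to one set of companion summaries. It does not rescue the IGA rule: the visible text neither restricts the Week 16 version to subjects who can attain it nor modifies the criterion, and for a subject at IGA 0 or 1 that reference is not applicable in any useful sense.

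Three stronger readings are tempting and are not supported:

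- *The report would count sustained clear skin as failure overall.* It would do so only in the Week 16-referenced version.
- *Up to 79% of re-randomised subjects are affected* (500 × 0.30 = 150 of 190). This divides a rate on all randomised subjects by a count built from 15% dropout and 45% response. It implies 190 of 500, or 38%, responding, below the 245 of 500 that 49% EASI-75 alone would give.
- *The OC-only outcomes break the protocol's rescue rule.* SAP 8.3 says "in OC analysis, all observed data even after the receipt of rescue treatment will be included for analysis", and the NRS below 2 subset is summarised "at each visit during the Maintenance Period will be summarized using OC", whereas Protocol 8.4.9.1.3 counts rescued subjects as treatment failures in efficacy analysis. But SAP 8.3 limits non-responder handling of missing binary data to the Initial Period and exempts OC from its rescue rule, and the maintenance period is descriptive. This supports an optional extra table, not a finding of departure.

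**Conclusion.** The point holds for the Week 16-referenced responder summaries. For IGA success it is a matter of arithmetic: subjects re-randomised at IGA 0 or 1 score non-success regardless of outcome. The pruritus NRS criterion has the same ceiling below 4, and the EASI versions measure further improvement rather than maintenance. The composites and the maintained-success rule need their reference stated.

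The 38% to 61% range, and the resulting cap of 39% to 62%, assume that the 30% and 49% planning rates hold on a common denominator; the overlap between them is unknown. The counts out of 190 are illustrative, since 190 itself comes from the 45% rate that does not fit with 49%. The consequence is an uninformative and possibly misleading descriptive table, worth correcting because the correction is nearly free. It does not touch any test, alpha, primary or key secondary result, or the Baseline-referenced maintenance outputs.

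**What to change.** 1. Use initial Baseline as the reference for maintenance responder outcomes, and say so for the maintained-response summaries and for both parts of each IGA or EASI plus itch composite.
2. Drop the Week 16-referenced IGA success and NRS improvement versions. Alternatively, restrict them to subjects who can attain them (Week 16 IGA of at least 2; Week 16 NRS of at least 4) and title them as further improvement.
3. Title Week 16-referenced EASI-50/75/90 as further improvement as well.
4. Keep continuous change from Week 16, which is interpretable as it stands.
5. Optional: for the OC-only ITT composites (SAP 10.3.1, 10.3.2) and the PP/AP NRS below 2 subset (SAP 10.3.3), add a version that counts rescue or missing data as non-response, in line with Protocol 8.4.9.1.3.

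The cost is SAP wording and a few table shells or titles. No new data are needed, and the descriptive status of the maintenance period does not change.

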10.3.2. Eczema Area and Severity Index (EASI)

The EASI is a validated measure commonly used in clinical trials and clinical practice to assess the severity and the extent of AD signs. The EASI score is a composite score ranging from 0 to 72 (see Table 6). The severity of erythema, induration/papulation, excoriation, and lichenification will be assessed by the investigator or trained designee on a scale of 0 (absent) to 3 (severe) for each of the 4 body areas: head/neck, trunk, upper limbs, and lower limbs, with half points allowed. In addition, the extent of AD involvement in each of the 4 body areas will be assessed as a percentage by body area of head, trunk, upper limbs, and lower limbs, and converted to a score of 0 to 6. The EASI score will be calculated (see Table 10-3).

Table 10-3: Eczema Area and Severity Index (EASI)

Body region	EASI score
Head/Neck (H)	$(E + I + Ex + L) \times \text{Area} \times 0.1$
Upper limbs (UL)	$(E + I + Ex + L) \times \text{Area} \times 0.2$
Trunk (T)	$(E + I + Ex + L) \times \text{Area} \times 0.3$
Lower limbs (LL)	$(E + I + Ex + L) \times \text{Area} \times 0.4$
EASI =	Sum of the above 4 body region scores

EASI-50, EASI-75 and EASI-90 are defined as a $\geq 50\%$, $\geq 75\%$, $\geq 90\%$ improvement in EASI from Baseline, respectively.

During Initial Period:

EASI will be collected at Screening, Baseline, Week 4, Week 8, Week 12, Week 16 and Early termination of the Initial Period.

EASI will be summarized as a continuous variable at each analysis visit. Absolute change and percent change from Baseline for the EASI score will also be included in the summary for ITT and PP population.

Change from Baseline in EASI at each analysis visit up to Week 16 will be analyzed using ANCOVA, with missing values imputed using MI under MAR assumption, and MMRM. For the MI and MMRM analyses the least squares means (LSMeans), standard error of LSMeans, and 95% CI for change from Baseline, as well as the difference in LSMeans between the treatment groups, the two-sided 95% CI, and associated p-value will be presented. In addition, percent change from Baseline in EASI at each analysis visit up to Week 16 will be analyzed using MMRM.

This document is confidential.

EASI-50/75/90 will be calculated using Baseline as the reference point for change in EASI score. The proportion of subjects achieving EASI-50/75/90 (OC, non-responder, LOCF) will be summarized on ITT population. And the results using OC will be provided for PP population.

For the proportion of subjects with EASI-50/75/90 (non-responder) and subjects with EASI-75 and PP NRS improvement ≥ 4 (non-responder), the estimate of treatment unadjusted and strata-adjusted differences with the corresponding 2-sided 95% confidence intervals, and p-values from the Cochran-Mantel-Haenszel test will be presented.

Line plot for proportion of subject with EASI-50/75/90 from Baseline using Non-responder imputation will be presented for Initial Period on the ITT population.

Individual components of the EASI score (averaged across body regions) will be summarized as continuous variables. Change from Baseline in individual components of the EASI score will also be presented in the summary table.

Change from Baseline in individual components of the EASI (averaged across body regions) at each analysis visit up to Week 16 will be analyzed using MMRM. For the MMRM analyses the least squares means (LSMeans), standard error of LSMMeans, and 95% CI for change from Baseline, as well as the difference in LSMMeans between the treatment groups, the two-sided 95% CI, and associated p-value will be presented.

During Maintenance Period:

EASI will be collected at Week 20, Week 24, Week 28, Week 32, Week 36, Week 40, Week 44, and Week 48 of the Maintenance Period.

EASI will be summarized as a continuous variable at each analysis visit. Absolute change and percent change from Baseline and Maintenance Baseline (Week 16) in EASI at each analysis visit up from Week 16 to Week 48 will also be summarized.

EASI-50/75/90 will be calculated using Baseline and Maintenance Baseline (Week 16) for change in EASI score. The proportion of subjects with EASI-50/75/90 will be summarized using OC, non-responder and LOCF.

Line plot for proportion of subject with EASI-50/75/90 from Baseline using Non-responder imputation will be presented for Maintenance Period on the ITT population.

For the subset of patients achieving EASI-75 at Week 16, the proportion of subjects maintaining EASI-75 at each visit throughout the Maintenance Period will be summarized. 'Maintaining EASI-75' is defined if a subject achieved EASI-75 at every analysis visits until the analysis visit summarized. For example, if a subject achieved EASI-75 until Week 28 except Week 24 then this subject will not be considered as "Subject maintaining EASI-75" at Week 28.

The number and percentage of subjects who achieved EASI-75 and an improvement of PP NRS ≥ 4 from Week 16 will be summarized for the ITT population using OC and for the subset of subjects with such a response at Week 16.

Individual components of the EASI score will be summarized as continuous variables. Change in individual components of the EASI score at each analysis visit from Week 16 to Week 48 will also be summarized.

This document is confidential.

No hypothesis testing will be performed.

